- ^c ECGs will be collected and read locally. All ECGs must be performed after the participant has been in a supine position for at least 5 minutes.
- ^d Chemistry, hematology, coagulation, and urinalysis at Screening and at all additional timepoints. Myoglobin (urinalysis) and serum creatine kinase (biochemistry) at Screening and at additional timepoints at the discretion of the investigator. A serum sample for blood alcohol level will be collected at Screening and all additional timepoints. HgA1c will be collected at Week 12 and Week 24.
- [REDACTED]
- ^f If a participant experiences AEs at any time during the Treatment Period that are considered by the investigator to be related to the IP and not tolerable, the investigator may reduce the dose of IP in 15 mg decrements. Self-administration of IP will be interrupted for 3 to 8 days before the initiation of the reduced dose.
- ^g Participants will self-administer on an outpatient basis a single dose of SAGE-324 once daily in the evening before bed, with a snack if bedtime is not within 2 hours of the evening meal.

Table 4: Schedule of Assessments: Month 9 to Follow-up Period

Assessment	Treatment Period						Follow-up Period	
	Month 9	Month 12	Month 15	Month 18	Month 21	Month 24 to Month 60 (Every 3 Months)	EOT 3 (± 3) days after last dose of SAGE-324	EOS 14 (± 3) days after last dose of SAGE-324
Study Month								
Window (Weeks)	± 2							
Pregnancy test	X (urine; WOCBP only)	X (urine; WOCBP only)	X (urine; WOCBP only)	X (urine; WOCBP only)				
Complete physical examination, including neurological examination including MSE ^a	X	X	X	X	X	X	X	X
Body weight ^b		X				X		X
Vital signs ^c	X	X	X	X	X	X	X	X
12-Lead ECG ^d	X	X	X	X	X	X	X	X
Chemistry/hematology/ coagulation/urinalysis ^e	X	X	X	X	X	X	X	X
C-SSRS ("Since Last Visit" form)	X	X	X	X	X	X	X	X
ESS	X	X	X	X	X	X	X	X
PWC-20							X	X
Dispense SAGE-324 ^f	X	X	X	X	X	X		

Assessment	Treatment Period						Follow-up Period	
	Month 9	Month 12	Month 15	Month 18	Month 21	Month 24 to Month 60 (Every 3 Months)	EOT 3 (± 3) days after last dose of SAGE-324	EOS 14 (± 3) days after last dose of SAGE-324
Study Month								
Window (Weeks)	± 2	± 2	± 2	± 2	± 2	± 2		
SAGE-324 accountability	X	X	X	X	X	X	X	X
SAGE-324 administration ^h	Administered once daily before bed							
AEs/SAEs	X							
Concomitant medication	X							

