5. INTRODUCTION

SAGE-324 is a positive allosteric modulator of A-type γ -aminobutyric acid-gated chloride channel (GABA_A) receptors, the major class of inhibitory neurotransmitter receptors in the brain. SAGE-324 is planned to be evaluated for multiple indications affected by activity at the GABA_A receptor, including essential tremor (ET).

Clinical studies of SAGE-324 in healthy adults and in adults with ET, in addition to preclinical studies of SAGE-324, are detailed in the SAGE-324 investigator's brochure as well as a detailed description of the chemistry, pharmacology, efficacy, and safety of SAGE-324.

ET is a common, permanently debilitating, neurologically determined movement disorder characterized by involuntary rhythmic oscillation of a body part due to intermittent muscle contractions. This shaking typically occurs during voluntary movement (ie, when not at rest), thus interfering with fine motor skills associated with daily activities (Olanow 2008, Deuschl 2011, Hopfner 2016, NIH 2019). Although the pathophysiology and etiology of ET is not fully understood, it is postulated that approximately 50% of ET patients feature an autosomal dominant pattern of familial inheritance and that noninherited cases may have toxin-based or other causality (Olanow 2008, Hopfner 2016). ET is the most common movement disorder in the US and worldwide, with prevalence estimated to be approximately 2.2% of the population, representing a substantial societal medical burden with over an estimated 7 million ET patients in the US alone (Louis 2014).

In general, active tasks of daily life are adversely impacted by ET, including but not limited to speech, handwriting, household tasks, and occupational demands, contributing negatively to psychosocial well-being, general anxiety, and overall quality of life (Koller, 1989). Although benign in terms of its effect on life expectancy, ET is a progressive neurodegenerative condition whose symptoms are typically disabling, often forcing patients to change jobs or seek early retirement (Zappia, 2013). In some cases, serious disability may ensue.

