Participants should gain experience with the study drug to see how it affects them before engaging in potentially hazardous activities requiring mental alertness, such as driving. If participants experience any sleepiness, dizziness, or feelings of relaxation, or have other sedative effects, they should not engage in potentially hazardous activities requiring mental alertness, such as driving, until any sleepiness/sedative effects from the study drug have dissipated. This is important because study participants may not be able to judge how these sedative effects will affect their ability to perform potentially hazardous activities requiring mental alertness, including driving.

The Treatment Period will continue for as long as the participant continues to self-administer SAGE-324 or until marketing authorization, projected to be up to approximately 5 years.

Follow-Up Period:

Follow-up visits will be conducted on an outpatient basis when participants have completed the Treatment Period. Participants will continue to complete questionnaires as indicated in [Table 4](#) and will return to the clinic 3 (± 3) days after the last dose of SAGE-324 for safety, tolerability, [REDACTED] at the End of Treatment (EOT) Visit. Participants will return to the study center for an End of Study (EOS) Visit, 14 (± 3) days after the last dose of SAGE-324.

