8.4.2. End of Study Activities

The duration of participation in this study is dictated by the duration of continued administration of IP. If the IP is permanently discontinued, two further study visits will be conducted: one approximately 3 days after IP discontinuation (EOT Visit) and another approximately 14 days after IP discontinuation (EOS Visit). If the participant does not attend the EOS Visit, they will be considered to be lost to follow-up.

If the participant withdraws consent for disclosure of future information, the sponsor will retain and continue to use any data collected before such a withdrawal of consent.

If a participant withdraws from the study, he/she may request destruction of any samples taken and not tested, and the investigator must document this in the site study records.

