12.1.8. Physician Withdrawal Checklist

The Physician Withdrawal Checklist (PWC) is based on the 35-item Penn Physician Withdrawal Checklist that was developed in the 1960s to measure benzodiazepine and benzodiazepine-like discontinuation symptoms. The PWC-20 is a shorter version of the Penn Physician Withdrawal Checklist based on the 20 items that provided the best differentiation from placebo in previous studies. The PWC-20 is made up of a list of 20 symptoms (eg, loss of appetite, nausea-vomiting, diarrhea, anxiety-nervousness, irritability) that are rated on a scale of 0 (not present) to 3 (severe) ([Rickels 2008](#)). The PWC-20 will be used to monitor for the presence of potential withdrawal symptoms after last dose of SAGE-324.

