8.4.7. Physician Withdrawal Checklist (PWC-20)

The PWC-20 is a shorter version of the Penn Physician Withdrawal Checklist based on the 20 items that provided the best differentiation from placebo in previous trials. The PWC-20

is made up of a list of 20 symptoms (eg, loss of appetite, nausea-vomiting, diarrhea, anxiety-nervousness, irritability) that are rated on a scale of 0 (not present) to 3 (severe) ([Rickels 2008](#)). The PWC-20 will be used to monitor for the presence of potential withdrawal syndrome following discontinuation of SAGE-324.

Summarization of PWC-20 data will be presented using the Safety Set – overall and by dose last received immediately prior to the evaluation. Descriptive statistics for the total PWC-20 score will be presented at End of Treatment (defined as the first available assessment after the last dose of study within 1 day of last dose) and End of Study. The change from End of Treatment to End of Study in PWC-20 total score will be provided. The number and percentage of participants with each PWC-20 item and reporting severe on a PWC-20 item will be presented at each visit. Descriptive statistics for the number of PWC-20 items and the number of severe PWC-20 items experienced at each visit will also be presented.

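### The PWC-20 is scheduled only after the last dose, so participants not scored within about a day of stopping have no on-drug reference, and the planned EOT-to-EOS change may be negative although withdrawal occurred

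*SAP*

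**What the plan says.** Protocol 12.1.8 gives the purpose: "The PWC-20 will be used to monitor for the presence of potential withdrawal symptoms after last dose of SAGE-324". In the schedule, Table 4 marks the PWC-20 in two columns only, headed "EOT 3 (± 3) days after last dose of SAGE-324" and "EOS 14 (± 3) days after last dose of SAGE-324". Tables 2 and 3, which cover Screening to Week 24, have no PWC-20 row, and the on-treatment columns of Table 4 are blank for it. Protocol 7.1 describes the same EOT visit: participants "will return to the clinic 3 (± 3) days after the last dose of SAGE-324". Protocol 9.5 confirms an open-label design, and every participant receives SAGE-324.

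SAP 4.2 lists PWC-20 responses and total score as a secondary endpoint, without a change from baseline. The other secondary endpoints in that list are all changes from baseline. SAP 8.4.7 summarises the total score at EOT and EOS, tabulates items and severe items at each visit, and adds one change score: "The change from End of Treatment to End of Study in PWC-20 total score will be provided". For this analysis the SAP gives EOT its own meaning: "defined as the first available assessment after the last dose of study within 1 day of last dose".

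**The concern.** Withdrawal means symptoms that appear or worsen after stopping, so measuring it needs either a score on drug or a comparison group. The schedule provides neither. The checklist covers symptoms such as anxiety, irritability, nausea and loss of appetite, which are not specific to withdrawal. The protocol's own introduction describes essential tremor as "contributing negatively to psychosocial well-being, general anxiety, and overall quality of life". A participant who stops because of an adverse event may also still have that event at the EOT visit.

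The one planned change takes EOT as its reference. At the nominal visit the participant has been off drug for 3 days. If withdrawal is already present then and eases by EOS, the change is negative. At stake is whether the study can answer its own question about withdrawal from a GABA-A modulator. The PWC-20 is the only measure in the visible text dedicated to that question.

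**Working it through.** The documents state no power, precision or event figure for the PWC-20, and the 750 participants are an exposure target, so there is no plan figure to reproduce. The check covers the schedule, the windows and the algebra of the change score.

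**1. Scale.** 20 items scored 0 to 3 give a total of 0 to 20 × 3 = 60.

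**2. Windows (protocol Table 4).** EOT is 3 ± 3, so day 0 to 6 after last dose. EOS is 14 ± 3, so day 11 to 17. The gap between them is 11 − 6 = 5 days at least, 14 − 3 = 11 nominally and 17 − 0 = 17 at most.

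**3. The two EOT definitions.** The SAP's 1-day limit covers days 0 and 1, which is 2 of the 7 window days. Nominal day 3 fails it. The distribution of visit days is not given, so two assumptions are shown:
- Visits spread evenly: 2/7 = 28.6%, or about 214 of 750 with a qualifying score and 536 without.
- Visits clustered on day 3 (assumed weights 0.02, 0.08, 0.20, 0.40, 0.20, 0.08, 0.02 for days 0 to 6): 0.02 + 0.08 = 10%, or 75 of 750 with a score and 675 without.

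These counts assume that all 750 attend EOT. Protocol 13.2 rules out imputation, so under the literal SAP rule those without an EOT score have no change score.

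**4. What the two scores can identify.** Let R be the unobserved on-drug score. The change from drug to EOT is EOT − R; the planned change is EOS − EOT, which does not contain R. With EOT 12 and EOS 6 the planned change is 6 − 12 = −6. If R = 5, the rise after stopping was 12 − 5 = +7. If R = 12, it was 0. The data are the same in both cases, and this does not depend on any assumed time course.

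**5. Sign of the change under an assumed course.** Take S(t) = b + A·[(t/p)·exp(1 − t/p)]³, with background b = 5, peak withdrawal excess A = 10 and peak on day p. All three are assumptions. Example with p = 3 and EOT on day 3: S(3) = 5 + 10 = 15; S(14) = 5 + 10 × 0.0017 = 5.02; change = −9.98, or −10.0. The true peak rise is +10 in every row below, with EOS on day 14.

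| Peak day | EOT day 1 | EOT day 3 | EOT day 6 |
|---|---|---|---|
| 1 | −10.0 | −0.7 | 0.0 |
| 2 | −5.6 | −7.5 | −0.7 |
| 3 | −2.7 | −10.0 | −4.0 |
| 5 | +0.1 | −6.2 | −8.5 |
| 7 | +3.6 | −0.4 | −5.7 |
| 10 | +8.1 | +6.1 | +1.1 |
| 14 | +9.9 | +9.0 | +5.6 |

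With EOT on day 3 the change is negative for peaks up to about one week. With EOT on day 1 a negative value needs a peak within about 3 days. The table shows that a negative change is possible. It does not estimate how often one would occur.

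**The case against.** **The SAP's 1-day rule gives a near-on-drug reference.** With once-daily dosing this is fair, and SAP 8.4.3 itself counts ECG values up to one day after last dose as on treatment. A reader might infer that withdrawal can never be told from background in this study. That is too strong: a participant scored on day 0 or 1 has a usable, if imperfect, reference. The point therefore holds only for the others. With a visit planned for day 3, they are likely to be the majority.

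**The SAP does not call the change a measure of withdrawal.** This stands. It says only that the change will be provided, shows EOT and EOS totals beside it, and tabulates items without calling them withdrawal cases. A reader might infer that the plan overstates withdrawal incidence; the documents claim no such incidence. The risk is in how the tables will be read.

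**The choice was deliberate.** The Amendment 1 log records that scores are not compared with baseline, which agrees with the current text. It gives no reason, and a pre-treatment baseline is a different thing from an on-treatment reference.

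**Other data help.** Adverse event onset dates, the C-SSRS, the ESS and the examinations at EOT and EOS give some separate information on new symptoms. They do not supply a reference for the PWC-20 score.

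**An on-treatment reference is imperfect too.** After Week 24 visits are quarterly, so the last score could be about 3 months old and predate the adverse event that led to stopping. Those symptoms would then look new after the last dose. This stands, and the fix has to allow for it.

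**Conclusion.** The point holds in limited form. For participants whose EOT score is not taken within about 1 day of last dose, post-dose PWC-20 scores cannot be separated from background symptoms or from the event that caused stopping, and the EOT-to-EOS change may be negative although withdrawal occurred. The ambiguity follows from the schedule alone. The size of any sign error rests on assumed scores and an assumed time course. The documents give no half-life figure and no withdrawal course, so they do not support a reading that the change usually has the wrong sign.

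Separately, the two EOT definitions conflict. Read literally, the SAP rule would leave most participants seen near day 3 without an EOT score or a change.

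The analysis is secondary and descriptive, and the primary endpoint (incidence of TEAEs) is not affected. Parts of the schedule are redacted, so the finding rests on the visible rows of protocol Tables 2 to 4 and on protocol 12.1.8.

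**What to change.** **Protocol.** Add the PWC-20 at a limited set of existing on-treatment visits, for example Week 12, Week 24 and the quarterly visits, all of which already include a complete examination. Add it also at any existing or unscheduled visit where the decision to stop is made while the participant is still on drug. The second addition limits the problem of an old reference.

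**SAP 8.4.7.**
- Reconcile the 1-day EOT definition with the protocol's day 3 ± 3 visit.
- Define the reference as the last PWC-20 on or before the date of last dose, and report how long before the last dose it was taken.
- Report the change from reference to EOT, to EOS and to the worst post-dose score, and the number and percentage with new or worse items.
- Show these separately for participants who stopped because of an adverse event, and for those with no reference or an old one.
- Describe the EOT-to-EOS change as recovery or time course only, and state that raw item counts are not withdrawal incidence.

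**Cost.** A protocol amendment and a few minutes per checklist, with no added scheduled visit. Month 9 to Month 60 contains (60 − 9)/3 + 1 = 18 quarterly visits. With Weeks 12 and 24 that makes at most 20 checklists per participant, or 20 × 750 = 15,000 if everyone stayed for the full 5 years; fewer visits could be chosen. The reference may still be up to about 3 months old, and participants already off drug cannot gain one. The SAP is dated 22 October 2024 and covers the final analysis. If on-treatment collection is no longer possible, the EOT reconciliation, the recovery label and the separate reporting of participants without a reference can still be done.

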8.4.8. Epworth Sleepiness Scale (ESS)

The ESS is a quick, 8-item, self-administered questionnaire where participants rate, on a 4-point scale of 0 (no chance of dozing) to 3 (high chance of dozing), their usual chances of dozing off or falling asleep while engaged in 8 different activities. The total ESS score estimates the participant's average sleep propensity, across a range of activities in their daily lives ([Johns 2002](#)).

All by-visit ESS summary tables will present results using the Safety Set – overall, and also by dose last received immediately prior to the evaluation. Descriptive statistics for each of the 8 individual items (continuous and by categorical response) at each scheduled visit, the total ESS score at each scheduled visit, and change from baseline in the total ESS score at each postbaseline visits will be presented. The number and percentage of participants with a total ESS score of 0, no chance of dozing off, will also be presented at each visit.

8.4.9. Other Safety Analysis

Not applicable.

8.6. Other Analysis

Not applicable.

9. SUMMARY OF INTERIM AND DMC ANALYSES

9.1. Interim Analysis

Not applicable.

9.2. DMC Analysis

Not applicable.

11. LIST OF APPENDICES

APPENDIX A. SCHEDULE OF ASSESSMENTS

Screening to Treatment Period Day 57

Assessment	Screening						Treatment Period					
	Study Day	-28 to -1	1	8	15	22	29	36	43	50	57	
Window (Days)			±2	±2	±2	±2	±2	±2	±2	±2	±2	
Informed consent	X											
Inclusion/Exclusion	X	X										
Demographics	X											
Medical history	X											
Pregnancy test	X	X	X	X	X	X	X	X	X	X	X	
FSH (postmenopausal women only)		X										
Drug screen	X	X										
Complete physical examination, including neurological examination including MSE ^a												
Body height	X											
Body weight	X											
Vital signs ^b	X	X	X	X	X	X	X	X	X	X	X	
12-Lead ECG ^c	X	X										
Chemistry/hematology/ coagulation/urinalysis ^d	X	X	X	X	X	X	X	X	X	X	X	

Assessment	Screening							Treatment Period				
	Study Day	-28 to -1	1	8	15	22	29	36	43	50	57	
Window (Days)			±2		±2		±2		±2		±2	±2
C-SSRS ("Screening/Baseline" form)		X										
C-SSRS ("Since Last Visit" form)			X	X	X	X	X	X	X	X	X	
ESS		X	X	X	X	X	X	X	X	X	X	
Participant training*		X	X									
Dispense SAGE-324 ^a			X	X	X	X	X	X	X	X	X	
SAGE-324 accountability				X	X	X	X	X	X	X	X	
SAGE-324 administration ¹												
AEs/SAEs ⁵												
Prior medication and history ⁴												
Concomitant medication												
Alcohol, nicotine products, and diet ^k												

Abbreviations: AE = adverse event; C-SSRS = Columbia-Suicide Severity Rating Scale; ECG = electrocardiogram; ESS = Epworth Sleepiness Scale; ET = essential tremor; FSH = follicle stimulating hormone; ICF = informed consent form; IP = investigational product; MSE = mental state examination; SAE = serious adverse event; WOCBP = women of childbearing potential.

Note: The suggested order of assessments during clinic visits is vital signs, [REDACTED] ECG, blood sample collection for [REDACTED] clinical laboratory assessments, and questionnaires.

Statistical Analysis Plan Methods Version 1.0 22Oct2024
Protocol Number: 324-ETD-303 (Version 4.0 02 Nov 2023)

Sage Therapeutics, Inc.
CONFIDENTIAL

- ^a Complete physical examination and a comprehensive neurological examination, including MSEs, should be performed at Screening and as clinically necessary (see Section 12.1.3). Targeted physical and neurological examinations should be performed at other times as indicated by AEs.
- ^b Vital signs comprise heart rate, respiratory rate, temperature, and blood pressure. Systolic and diastolic blood pressure are to be measured after the participant has been supine for at least 5 minutes prior to the measurement. Orthostatic blood pressure and heart rate will also be measured after the participant has been in the supine position for at least 5 minutes and then repeated approximately 1 and 3 minutes after standing. On Day 1, supine and standing blood pressure and heart rate will be collected in triplicate at least 15 minutes apart, measured after the participant has been in the supine position for at least 5 minutes and then repeated 1 minute and 3 minutes after standing. Respiratory rate and temperature are collected once on Day 1.
- ^c ECGs will be collected and read locally. All ECGs must be performed after the participant has been in a supine position for at least 5 minutes.
- ^d Chemistry, hematology, coagulation, and urinalysis at Screening and at all additional timepoints. Myoglobin (urinalysis) and serum creatine kinase (biochemistry) at Screening and at additional timepoints at the discretion of the investigator. A serum sample for blood alcohol level will be collected at Screening and all additional timepoints. HbA1c will be collected at Screening.
- At the discretion of the investigator, clinical laboratory assessments from another SAGE-324 study may be used to determine eligibility for this study if within 28 days of Day 1.

^g Participants will be trained by study personnel on the use of software applications, IP diary, and devices necessary for the conduct of the study.

^h Participants will self-administer orally 15 mg SAGE-324 on Day 1 to Day 14, 30 mg on Day 15 to Day 28, 45 mg on Day 29 to Day 42, and then 60 mg daily starting on Day 43. If a participant experiences AEs that are considered at any time in the Treatment Period by the investigator to be related to the IP and not tolerable, the investigator may reduce the dose of IP in 15 mg decrements, including during the initial dose escalation period. Self-administration of IP will be interrupted for 3 to 8 days before the initiation of the reduced dose.

ⁱ Participants will self-administer orally on an outpatient basis a single dose of SAGE-324 once daily in the evening before bed, with a snack if bedtime is not within 2 hours of the evening meal.

^j Including all medications and supplements taken within the 30 days prior to signing the ICF through the first dose of SAGE-324, as well as a complete history of all treatments for ET since the year of diagnosis.

^k Alcohol, nicotine use and diet will be collected to ensure compliance with IC#9, IC#10, and EC#14, respectively.

Treatment Period Week 10 to Week 24

Assessment	Treatment Period					
	10	12	16	20	24	
Study Week						
Window (Weeks)	±1	±1	±1	±1	±1	
Pregnancy test	X	X	X	X	X	
	(urine; WOCBP only)	(urine; WOCBP only)				
Complete physical examination, including neurological examination including MSE ^a		X				X
Vital signs ^b	X	X	X	X	X	
12-Lead ECG ^c		X	X		X	
Chemistry/hematology/ coagulation/urinalysis ^d		X	X		X	
C-SSRS ("Since Last Visit" form)	X	X	X	X	X	
ESS		X	X	X	X	X
Dispense SAGE-324 ^e		X	X	X	X	X
SAGE-324 accountability		X	X	X	X	X
SAGE-324 administration ^f					Administered once daily before bed	
AEs/SAEs					X	
Concomitant medication					X	

Abbreviations: AE = adverse event; C-SSRS = Columbia-Suicide Severity Rating Scale; ECG = electrocardiogram; ESS = Epworth Sleepiness Scale; IP = investigational product; MSE = mental state examination; [REDACTED] = serious adverse event; [REDACTED] = SAE = serious adverse event; [REDACTED] = blood sample collection for [REDACTED] ECG, blood sample collection for [REDACTED] clinical laboratory

Note: The suggested order of assessments during clinic visits is vital signs, [REDACTED] ECG, blood sample collection for [REDACTED] assessments, and questionnaires.

Statistical Analysis Plan Methods Version 1.0 22Oct2024
Protocol Number: 324-ETD-303 (Version 4.0 02 Nov 2023)

Sage Therapeutics, Inc.
CONFIDENTIAL

^a Complete physical examination and a comprehensive neurological examination, including MSEs, should be performed as clinically necessary (see Section 12.1.3). Targeted physical and neurological examinations should be performed as indicated by AEs.

^b Vital signs comprise heart rate, respiratory rate, temperature, and blood pressure. Systolic and diastolic blood pressure are to be measured after the participant has been supine for at least 5 minutes prior to the measurement. Orthostatic blood pressure and heart rate will also be measured after the participant has been in the supine position for at least 5 minutes and then repeated approximately 1 and 3 minutes after standing.

^c ECGs will be collected and read locally. All ECGs must be performed after the participant has been in a supine position for at least 5 minutes.

^d Chemistry, hematology, coagulation, and urinalysis at Screening and at all additional timepoints. Myoglobin (urinalysis) and serum creatine kinase (biochemistry) at Screening and at additional timepoints at the discretion of the investigator. A serum sample for blood alcohol level will be collected at Screening and all additional timepoints. HbA1c will be collected at Week 12 and Week 24.

^e If a participant experiences AEs at any time during the Treatment Period that are considered by the investigator to be related to the IP and not tolerable, the investigator may reduce the dose of IP in 15 mg decrements. Self-administration of IP will be interrupted for 3 to 8 days before the initiation of the reduced dose.

^g Participants will self-administer on an outpatient basis a single dose of SAGE-324 once daily in the evening before bed, with a snack if bedtime is not within 2 hours of the evening meal.

Month 9 to Follow-up Period

Assessment	Treatment Period						Follow-up Period	
	Study Month	Month 9	Month 12	Month 15	Month 18	Month 21	Month 24 to Month 60 (Every 3 Months)	EOT 3 (± 3) days after last dose of SAGE-324
Window (Weeks)	± 2							
Pregnancy test	X (urine; WOCBP only)	X (urine; WOCBP only)						
Complete physical examination, including neurological examination including MSE ^a	X	X	X	X	X	X	X	X
Body weight ^b		X				X		X
Vital signs ^c	X	X	X	X	X	X	X	X
12-Lead ECG ^d	X	X	X	X	X	X	X	X
Chemistry/hematology/ coagulation/urinalysis ^e	X	X	X	X	X	X	X	X
C-SSRS ("Since Last Visit" form)	X	X	X	X	X	X	X	X
ESS	X							
PWC-20								
Dispense SAGE-324 ^f	X	X	X	X	X	X	X	X

Assessment	Treatment Period						Follow-up Period	
	Month 9	Month 12	Month 15	Month 18	Month 21	Month 24 to Month 60 (Every 3 Months)	EOT 3 (± 3) days after last dose of SAGE-324	EOS 14 (± 3) days after last dose of SAGE-324
Window (Weeks)	± 2	± 2	± 2	± 2	± 2	± 2		
SAGE-324 accountability	X	X	X	X	X	X	X	X
SAGE-324 administration ^b								
AEs/SAEs								
Concomitant medication								

Abbreviations: AE = adverse event; C-SSRS = Columbia Suicide Severity Rating Scale; ECG = electrocardiogram; EOS = End of Study; EOT = End of Treatment; IP = investigational product; MSE = mental state examination; PWC-20 = 20-item Physician Withdrawal Checklist; SAE = serious adverse event; [REDACTED]

[REDACTED] WOCBP = women of childbearing potential.

Note: The suggested order of assessments during clinic visits is viral signs, [REDACTED] ECG, blood sample collection for [REDACTED] clinical laboratory assessments, and questionnaires.

^a Complete physical examination and a comprehensive neurological examination, including MSEs, should be performed as clinically necessary (see Section 12.1.3). Targeted physical and neurological examinations should be performed as indicated by AEs.

^b Weight assessed annually.

^c Vital signs comprise heart rate, respiratory rate, temperature, and blood pressure. Systolic and diastolic blood pressure are to be measured after the participant has been supine for at least 5 minutes prior to the measurement. Orthostatic blood pressure and heart rate will also be measured after the participant has been in the supine position for at least 5 minutes and then repeated approximately 1 and 3 minutes after standing.

^d ECGs will be collected and read locally. All ECGs must be performed after the participant has been in a supine position for at least 5 minutes.

^e Chemistry, hematology, coagulation, and urinalysis at Screening and at all additional timepoints. Myoglobin (urinalysis) and serum creatine kinase (biochemistry) at Screening and at additional timepoints at the discretion of the investigator. A serum sample for blood alcohol level will be collected at Screening and all additional timepoints. HbA1c will be collected at every other scheduled visit.

^g If a participant experiences AEs at any time during the Treatment Period that are considered by the investigator to be related to the IP and not tolerable, the investigator may reduce the dose of IP in 15 mg decrements. Self-administration of IP will be interrupted for 3 to 8 days before the initiation of the reduced dose.

^h Participants will self-administer on an outpatient basis a single dose of SAGE-324 once daily in the evening before bed, with a snack if bedtime is not within 2 hours of the evening meal.

Statistical Analysis Plan Methods Version 1.0 22Oct2024
Protocol Number: 324-ETD-303 (Version 4.0 02 Nov 2023)

Sage Therapeutics, Inc.
CONFIDENTIAL

